7.8.3 Laboratory Evaluations

Data for hematology, blood chemistry, and urinalysis analytes received from central laboratory/recorded in the eCRF will be listed and summarized by treatment group and overall for each scheduled collection visit. Standard descriptive statistics (see [Table 1](#)) will be presented for the observed values and change from baseline. Baseline definition can be found in [section 3.1](#).

A laboratory value that is within the central laboratory's reference range will be considered normal. A laboratory value that is outside the central laboratory's normal range will be considered abnormal and will be flagged as either high (H) or low (L). The number and percentage of subjects with abnormal laboratory values will be summarized for each analyte for each scheduled visit. Shift tables will be presented to display the shift in the normal range categories (low, normal, high) from baseline to each post-baseline visit for the following laboratory evaluations: hemoglobin, hematocrit, prothrombin time, activated partial thromboplastin time, total bilirubin, alkaline phosphatase, aspartate aminotransferase (AST), alanine aminotransferase (ALT), and creatinine.

Additionally, the number and percentage of subjects with clinically significant laboratory values will be summarized for each analyte for each scheduled visit.

The following analytes will be included in the analysis:

Statistical Analysis Plan

Sponsor Name: Anthos
Sponsor Protocol ID: ANT-004

Covance Study ID: 000000189471

Hematology	Serum Chemistry	Urinalysis (dipstick)
Hemoglobin	Sodium	Specific Gravity
Hematocrit	Potassium	Protein
Red Blood Cell Count	Creatinine	Glucose
Platelets	Blood Urea Nitrogen	White Blood Cell Count
Neutrophils	Uric acid	Red blood Cell Count
Lymphocytes	Chloride	
Monocytes	Albumin	
Eosinophils	Calcium	
Basophils	Alkaline phosphatase	
Leukocytes	Total Bilirubin	
Activated Partial Thromboplastin Time (aPTT) -FSL	Direct Bilirubin*	
Prothrombin Time (PT)	Indirect Bilirubin*	
International Normalized Ratio (INR)	Bicarbonate	
	Lactate Dehydrogenase (LDH)	
	Gamma-Glutamyltransferase (GGT)	
	Aspartate aminotransferase (AST)	
	Alanine aminotransferase (ALT)	
	Creatine Kinase (CK)	
	Glucose	
	Total Cholesterol	
	Triglycerides	

*if Total Bilirubin >1.5x upper limit of normal

All clinical laboratory data will be presented in listings. Laboratory data will be summarized in SI units.

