7.10 Clinical Laboratory Evaluations

Clinically relevant deviations of laboratory test results occurring during or at completion of the study must be reported and discussed with Covance personnel. The results should be evaluated for criteria defining an AE and reported as such if the criteria are met. Repeated evaluations are mandatory until normalization of the result(s) or until the change is no longer clinically relevant. In case of doubt, Covance personnel should be contacted.

Safety labs (hematology, clinical chemistry and urinalysis) do not need to be repeated at baseline if the Baseline visit is taking place within 48 hours of the screening labs being collected from an individual subject.

Subjects should be instructed to fast for at least 8 hours prior to scheduled safety lab collections.

Clinically notable laboratory findings are defined in [Appendix 3](#).

Hematology

Hemoglobin, hematocrit, red blood cell (RBC) count, white blood cell (WBC) count with differentials and platelet count will be measured.

Clinical chemistry

Sodium, potassium, creatinine, BUN/urea, uric acid, chloride, albumin, calcium, alkaline phosphatase, total bilirubin, bicarbonate/HCO₃, LDH, GGT, AST, ALT, CK, glucose, total

cholesterol, triglycerides. If the total bilirubin concentration is increased above 1.5 times the upper limit of normal, direct and indirect reacting bilirubin should be differentiated.

Urinalysis

Measurements for specific gravity, protein, glucose and blood will be performed. Microscopy, WBC, RBC and sediments will also be assessed in case of an abnormal test result.

Special clinical laboratory evaluations

Stool samples will be collected to check for occult blood at screening and baseline. Screening fecal samples can be collected at any time during the Screening period, and baseline fecal samples must be collected within 72 hours of Day 1. If fecal screening samples are collected within 72 hours of Day 1, then they do not need to be repeated for the Baseline visit. In the event that a subject is unable to produce a stool sample for sampling, the site medical staff may elect to produce a sample via digital extraction from the rectum.

Details regarding collection methods and processing are outlined in the Central Laboratory Manual.

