12.2. Appendix 2 - Specific Renal Alert Criteria and Actions

Table 7: Specific Renal Alert Criteria and Actions

Criteria	Action required
Serum creatinine (sCr) increase 25 – 49% compared to baseline	
 • Consider causes and possible interventions • Follow up within 2-5 days
Serum creatinine increase \geq 50%	
 • Consider causes and possible interventions • Repeat assessment within 24-48 hours if possible • Consider hospitalization and specialized treatment
Protein-creatinine or albumin-creatinine ratio increase \geq 2-fold, or new onset proteinuria \geq 1+ , or Albumin-creatinine ratio (ACR) \geq 30 mg/g or \geq 3 mg/mmol, or Protein-creatinine ratio (PCR) \geq 150 mg/g or $>$ 15 mg/mmol	
 • Consider causes and possible interventions • Assess serum albumin and serum protein • Repeat assessment to confirm
New onset glucosuria on urine exam (unless related to concomitant treatment, diabetes)	
Assess and document:
 
 • Blood glucose (fasting) • Serum creatinine • Urine albumin-creatinine ratio
New hematuria on urine exam	
Assess and document
 
 • Urine sediment microscopy • Assess sCr and urine albumin-creatinine ratio • Exclude infection, trauma, bleeding from the distal urinary tract/bladder, menstruation • Consider bleeding disorder

Additional specialized assessments are available to assess renal function or renal pathology.

(Note: In exceptional cases when a nephrologist considers a renal biopsy, it is strongly recommended to make specimen slides available for evaluation by Anthos to potentially identify project-wide patterns of nephrotoxicity.)

Whenever a renal event is identified, a detailed subject history and examination are indicated to identify, document and potentially eliminate risk factors that may have initiated or contributed to the event:

- Blood pressure assessment (after 5 min rest, with an appropriate cuff size)
- Signs and symptoms such as fever, headache, shortness of breath, back or abdominal pain, dysuria, hematuria, dependent or periorbital edema
- Changes in blood pressure, body weight, fluid intake, voiding pattern, or urine output

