12.4. Appendix 4 - Schedule of Assessments

Table 9: Schedule of Assessments

Period	Screening	Treatment							Washout / Follow-up			
Visit	1	2	3	4	5	6	7	8	9	10	TD	EoS
Day	-28 to -3	1 (predose)	11	31 (predose)	41	61 (predose)	71	91	101	121	-	170
Window			±2	±2	±3	±2	±3	±2	±3	±3		±10
Informed consent	X											
Medical history	X											
Drug & alcohol screen	X											
I/E criteria	X	X										
Physical Exam	X	X	X	X		X		X		X	X	X
Height	X											
Weight	X	X										X
Vital signs	X	X	X	X	X	X	X	X	X	X	X	X
12-lead ECG	X	X						X				X
HIV, Hepatitis B, Hepatitis C	X											
aPTT, Free and total FXI	X	X	X	X	X	X	X	X	X	X	X	X
aPTT (corrected for FXI), FXI:C		X				X		X				X
PK assessment: total MAA868		X	X	X	X	X	X	X	X	X		X
Antidrug antibodies (ADA)		X		X		X	X	X		X		X
Exploratory biomarker collection	X	X		X		X		X		X		
Complete safety Labs	X	X	X	X	X	X		X		X	X	X
Pregnancy test	Serum	Urine			Urine			Urine			Urine	Urine
Urine	X	X	X	X	X	X		X		X	X	X
Fecal occult blood test	X	X										
AE collection						X						
Concomitant meds						X						
Local assessment of CV and cerebrovascular events							X					
Local assessment of bleeding events							X					
Dispense Study Medications		X		X		X						
Drug Accountability		X		X		X		X				
MAA868		X		X		X						
Placebo		X		X		X						

Period	Screening	Treatment							Washout / Follow-up			
Visit	1	2	3	4	5	6	7	8	9	10	TD	EoS
Day	-28 to -3	1 (predose)	11	31 (predose)	41	61 (predose)	71	91	101	121	-	170
Window			±2	±2	±3	±2	±3	±2	±3	±3		±10
Injection site inspection (post-dose)		X	X	X	X	X	X					
Study disposition								X			X	X

TD = Study treatment discontinuation; EoS = End of Study; FXI:C = Factor XI coagulation activity

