7.10. Clinical Laboratory Evaluations

Clinically relevant deviations of laboratory test results occurring during or at completion of the study must be reported and discussed with Covance personnel. The results should be evaluated for criteria defining an AE and reported as such if the criteria are met. Repeated evaluations are mandatory until normalization of the result(s) or until the change is no longer clinically relevant. In case of doubt, Covance personnel should be contacted.

Safety labs (hematology, clinical chemistry and urinalysis) do not need to be repeated at baseline if the Baseline visit is taking place within 48 hours of the screening labs being collected from an individual subject.

Subjects should be instructed to fast for at least 8 hours prior to scheduled safety lab collections.

Clinically notable laboratory findings are defined in [Appendix 3](#).

Hematology

Hemoglobin, hematocrit, red blood cell (RBC) count, white blood cell (WBC) count with differentials and platelet count will be measured.

Clinical chemistry

Sodium, potassium, creatinine, BUN/urea, uric acid, chloride, albumin, calcium, alkaline phosphatase, total bilirubin, bicarbonate/HCO₃, LDH, GGT, AST, ALT, CK, glucose, total cholesterol, triglycerides. If the total bilirubin concentration is increased above 1.5 times the upper limit of normal, direct and indirect reacting bilirubin should be differentiated.

Urinalysis

Dipstick measurements for specific gravity, protein, glucose and blood will be performed. Microscopy, WBC, RBC and sediments will also be assessed in case of an abnormal dipstick test.

Special clinical laboratory evaluations

Stool samples will be collected to check for occult blood at screening and baseline. Screening fecal samples can be collected at any time during the Screening period, and baseline fecal samples must be collected within 72 hours of Day 1. If fecal screening samples are collected within 72 hours of Day 1, then they do not need to be repeated for the Baseline visit. In the event that a subject is unable to produce a stool sample for sampling, the site medical staff may elect to produce a sample via digital extraction from the rectum.

Details regarding collection methods and processing are outlined in the Central Laboratory Manual.

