Sponsor Name: Anthos
Sponsor Protocol ID: ANT-004

Covance Study ID: 000000189471

1. Source Documents

The Statistical Analysis Plan (SAP) was written based on the following documentation:

Document	Date	Version
Protocol	01-November-2019	Version 2.0
Electronic Case Report Form (eCRF)	27-March-2020	Version 1.0

2. Protocol Details

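### SAP 7.8.3 leaves urine blood, a routine protocol test, out of its urinalysis list and does not mark urine WBC and RBC as conditional tests

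*SAP*

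**What the plan says.** **Current protocol (Amendment 2), 7.10, Urinalysis.** The routine tests are: "Measurements for specific gravity, protein, glucose and blood will be performed". The conditional tests are: "Microscopy, WBC, RBC and sediments will also be assessed in case of an abnormal test result".

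**Protocol version 2.0 (Amendment 1), 7.10.** SAP section 1 names this version, dated "01-November-2019", as its source. Its content is the same: "Dipstick measurements for specific gravity, protein, glucose and blood will be performed", then "Microscopy, WBC, RBC and sediments will also be assessed in case of an abnormal dipstick test".

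**Protocol Appendix 4, "Table 9: Schedule of Assessments".** The urine row is marked at Screening, Days 1, 11, 31, 41, 61, 91 and 121, treatment discontinuation and end of study. It is blank at Days 71 and 101.

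**Protocol Appendix 2, Table 7.** The renal alert criteria include "New hematuria on urine exam", and considering a bleeding disorder is among the listed actions.

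**SAP 7.8.3.** The section introduces a table as the set of analytes for analysis. The column "Urinalysis (dipstick" contains specific gravity, protein, glucose, white blood cell count and red blood cell count. In the chemistry column, direct and indirect bilirubin carry an asterisk saying that they exist only when total bilirubin exceeds a threshold. The urine cell counts carry no such mark. Abnormal values are to be counted per analyte and per scheduled visit.

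**SAP 7.1, Table 1.** The default denominator for percentages is the whole analysis set unless a table shell says otherwise. A missing category is shown when any value is missing.

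**SAP section 8.** No changes from the protocol's planned analyses are declared.

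**The concern.** The SAP list replaces a test done on every routine sample with two tests done only on samples that have already given an abnormal result. Protocol 8.6 (Clinical Laboratory Evaluations) plans a summary of abnormal laboratory values at each scheduled visit. If the SAP list is followed, urine blood drops out of that summary without being declared as a change.

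The analyte bears on the drug's main safety question. Bleeding is a secondary safety objective (protocol 2.2). Protocol 1.1 names the urinary tract among the tissues preferentially affected by bleeding in severe Factor XI deficiency. Urine blood is also a laboratory result collected on schedule, so it does not depend on a subject reporting symptoms or an investigator deciding to report an event.

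**Working it through.** The check compares two lists, counts visits and asks what the retained rows can estimate. The plan gives no figure to reproduce.

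**Step 1: compare the lists.**

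| Urine analyte | Protocol 7.10 (both versions) | SAP 7.8.3 list |
|---|---|---|
| Specific gravity | Routine | Listed |
| Protein | Routine | Listed |
| Glucose | Routine | Listed |
| Blood | Routine | Not listed |
| White blood cells | Only after an abnormal result | Listed, not flagged |
| Red blood cells | Only after an abnormal result | Listed, not flagged |

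Routine in the protocol but not in the SAP list: {blood}. In the SAP list but only conditional in the protocol: {white cells, red cells}. Version 2.0 and Amendment 2 agree on this, so the SAP's older source version does not explain the omission.

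**Step 2: count the visits (Table 9, urine row).**
- All columns: 12, of which 10 are marked.
- Scheduled visits, leaving out treatment discontinuation: 11, of which 9 are marked.
- Scheduled post-baseline visits (Days 11, 31, 41, 61, 71, 91, 101, 121, 170): 9, of which 7 are marked. The two gaps are Days 71 and 101.

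**Step 3: what the red cell row would show.** For one arm at one visit, let N be the subjects in the analysis set, M those with a urine blood result, B those positive for blood, T those with a reflex red cell result, and A those whose red cell result is abnormal.
- The incidence of interest among subjects tested is B/M.
- The SAP default is A/N. The N − T subjects with no red cell result sit in the denominator, as not abnormal or as missing. They mix subjects whose routine test was normal with subjects who gave no sample, and the row cannot separate them.
- If a table shell used subjects tested, the result would be A/T, in a group selected because some urine result was abnormal.
- A need not equal B. A sample positive for blood can have a normal red cell result, and the reflex can be triggered by protein or glucose rather than blood.

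Neither A/N nor A/T is B/M. The documents do not fix the direction of the difference.

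**Step 4: whether other planned outputs fill the gap.**
- *Adverse events (protocol 7.6.1; SAP 7.8.2).* An abnormal laboratory result counts only if it causes signs or symptoms, is judged clinically significant or needs therapy. Asymptomatic urine blood may meet none of these.
- *Adjudicated bleeding (protocol Appendix 5; SAP 7.8.8).* The haematuria example for clinically relevant non-major bleeding is macroscopic.
- *Shift tables (SAP 7.8.3).* Nine laboratory measures are named, none of them urinary.
- *Listings (SAP 7.8.3).* All laboratory data are listed, so the blood results are visible by subject, but a listing gives no count by arm.

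**The case against.** Four arguments on the other side carry weight.

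**The signal is partly tabulated already.** An abnormal blood result triggers the red cell assessment, so the red cell row carries part of it. Haematuria that qualifies as an adverse event or an adjudicated bleed is tabulated by arm, and everything is listed. This stands. A reader might infer from the omission that haematuria is never summarised by arm, and the documents do not support that. What is missing is the by-visit, by-arm summary of urine blood among all subjects tested.

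**The red cell row may be the dipstick blood result under another name.** It sits under a dipstick heading, and neither the eCRF nor the Central Laboratory Manual is available to settle the question. This cannot be excluded. On that reading the result is mislabelled rather than dropped, and the table still needs correcting.

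**The opening sentence of 7.8.3 is broad.** It promises summaries of the urinalysis analytes received, and a programmer could take that to include blood. The explicit list that follows is narrower, so the section then conflicts with itself.

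**Urine blood is non-specific and is not a named endpoint.** Table 7 tells sites to exclude infection, trauma, a distal urinary source and menstruation. This stands too, and it limits the importance of the point.

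A further inference to resist is that the red cell table would overstate the positive fraction because only abnormal samples reach it. The default denominator is the whole analysis set, not the samples tested. The reflex follows any abnormal urine result, so even the tested group is not all blood-positive.

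**Conclusion.** The point holds and is minor. The SAP's stated list omits one of the four routine urine tests and includes two conditional tests without saying so, while section 8 declares no departure from the protocol. The omission affects 9 of 11 scheduled visits, 7 of them post-baseline. Asymptomatic microscopic haematuria could be collected on schedule and appear only in a listing or, in part, in a red cell row that does not estimate its incidence.

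The conclusion assumes that the SAP list is followed literally, that the red cell row is the reflex test described in protocol 7.10, and that no table shell, which the documents do not include, adds urine blood or changes the denominator. If the second assumption fails, the defect is one of labelling. Data collection, the primary endpoint and the adjudicated bleeding analysis are unaffected.

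**What to change.** In SAP 7.8.3:

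1. Add blood to the urinalysis column. Tabulate it as a categorical result by visit and treatment group, with the number of subjects tested as the denominator and baseline status shown so that new positives can be identified. If the red cell row is in fact the dipstick blood result, relabel it and give it the same summary.
2. Footnote urine white and red cells as reflex tests, as the table already does for direct and indirect bilirubin, and report the number tested at each visit.
3. Reword the column heading so that it does not describe reflex tests as dipstick results.

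The cost is one added analyte, one footnote and one table layout in a SAP amendment. Showing baseline status goes slightly beyond restoring the omitted row, because the SAP plans no urinary shift table, but it uses results already scheduled at Screening and Day 1. No new data collection is needed.

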7.8.4 Vital Signs

The following vital signs will be summarized by treatment group and overall for each scheduled collection visit. Standard descriptive statistics (see [Table 1](#)) will be presented for the observed values and change from baseline. Baseline definition can be found in [section 3.1](#). Vital signs results will be listed for each subject by treatment group for each scheduled collection visit.

- Sitting diastolic blood pressure (mmHg)

CONFIDENTIAL

Page 23 of 28

Statistical Analysis Plan

Sponsor Name: Anthos
Sponsor Protocol ID: ANT-004

Covance Study ID: 000000189471

- Sitting systolic blood pressure (mmHg)
- Heart rate (bpm)
- Temperature (°C)
- Weight (kg)

7.8.5 Electrocardiograms (ECG)

The following ECG measures will be summarized by treatment group and overall for each scheduled collection visit. Standard descriptive statistics (see [Table 1](#)) will be presented for the observed values. Baseline definition can be found in [section 3.1](#). ECG results will be listed for each subject by treatment group for each scheduled collection visit.

- Heart rate (bpm)
- Fridericia corrected QT (QTcF) interval (msec)
- QT interval (msec)
- RR interval (msec)
- PR interval (msec)
- QRS interval (msec)

An overall investigator interpretation of ECG will be provided (categories “normal”, “abnormal, not clinically significant” and “abnormal, clinically significant”). Subjects with abnormal ECG results, as judged by the investigator, will also be listed.

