4. SELECTION OF STUDY POPULATION

4.1. Inclusion Criteria

1. Written informed consent must be obtained before any assessment is performed
2. Male and female patients ≥ 18 and < 85 years old with paroxysmal atrial fibrillation (PAF) or atrial flutter on 12 lead electrocardiography at Screening Or
3. Patients with a history of PAF or atrial flutter, as documented by (telemetry, 12 lead electrocardiography or ambulatory [e.g. Holter] monitor) and not due to a reversible condition (e.g. alcohol binge drinking) can be entered even if they do not have PAF at Screening. There is not time-limit for this.
4. Patients with a CHA2DS2-VASc risk score (tool as a predictor for estimating the risk of stroke in patients with AF; Lip et al 2010) of 0-1 for men and 1-2 for women and in whom, in the investigator's judgment, the use of an anticoagulant for stroke prevention is not indicated
5. Body weight between 50 and 130 kg inclusive

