Vital Sign Measurements

Pre-dose values, post-dose values, and the change from baseline in vital sign measurements (sitting diastolic and systolic blood pressure, pulse, temperature and body weight) will be summarized with descriptive statistics (n, mean, SD, median, min, and max) at each timepoint by treatment. The baseline value will be value just prior to first administration of study medication.

ECG Parameters

The ECG measures (QTc-F, QT, RR, ventricular rate, PR, and QRS) will be listed and summarized with descriptive statistics (n, mean, SD, median, min, and max) at each timepoint by treatment.

The listings of subjects with abnormal ECG results, as judged by the Investigator, will be displayed and will be calculated. The baseline will be the value just prior to first administration of study medication.

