7.8.6 Physical Examination

Physical exams will include assessment of the following body systems:

- General appearance
- Skin
- Lymph nodes
- Head, eyes, ear, nose, and throat
- Neck
- Thorax/lungs
- Cardiovascular
- Abdomen
- Musculoskeletal
- Neurological

Physical examination results (normal/abnormal) and details of abnormalities will be listed for each subject. For each physical examination body system, the number and

CONFIDENTIAL

Page 24 of 28

percentage of subjects with abnormalities will be summarized by treatment group and overall for each scheduled visit where the examination is performed.

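### SAP 7.8.5 and 7.8.6 plan no change-from-baseline or shift summary for ECG and physical examination, so the tables cannot separate new from pre-existing abnormalities

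*SAP*

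**What the plan says.** **ECG (SAP 7.8.5).** Six measures (heart rate, QTcF, QT, RR, PR, QRS) are summarised by treatment group and visit, and the statistics "will be presented for the observed values". The section continues: "Baseline definition can be found in" section 3.1. Section 3.1 is the Primary Endpoint; the baseline definition is in 6.1. No ECG summary then uses a baseline. "An overall investigator interpretation of ECG will be provided", in three categories (normal, abnormal not clinically significant, abnormal clinically significant), with no shift table. "ECG results will be listed for each subject by treatment group for each scheduled collection visit", and abnormal ECGs are listed separately.

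**Physical examination (SAP 7.8.6).** Results and details of abnormalities are listed by subject. For each body system, the number and "percentage of subjects with abnormalities will be summarized by treatment group and overall for each scheduled visit where the examination is performed".

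**Protocol 8.6, ECG Parameters.** Descriptive statistics by timepoint are requested, and a baseline is defined without being used: "The baseline will be the value just prior to first administration of study medication".

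**Neighbouring SAP sections.** Laboratory values (7.8.3) get change from baseline, with shift tables for selected tests. Vital signs (7.8.4) get change from baseline. Both carry the same wrong pointer to section 3.1.

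**Population (Protocol 4.1).** Criterion 2 takes subjects with "paroxysmal atrial fibrillation (PAF) or atrial flutter on 12 lead electrocardiography at Screening". Criterion 3 also admits subjects by documented history alone.

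**The concern.** Many subjects may have an abnormal ECG or cardiovascular examination before any drug is given. What a safety reader wants to know is who changed after dosing. A table of the number abnormal at each visit does not answer that, because the same total can come from the same people staying abnormal or from different people becoming abnormal.

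Protocol Table 9 schedules ECGs at Screening, Day 1 predose, Day 91 and end of study only. Each subject therefore has one scheduled treatment-period ECG after dosing, and pairing it with baseline is the natural summary. The SAP gives no reason for handling ECG and examination differently from laboratory values and vital signs, and a baseline that is cited but unused suggests an oversight.

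At stake is how clearly descriptive safety data can be read in arms of 12 MAA868 and 4 placebo subjects per cohort. The primary endpoint is not affected.

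**Working it through.** The documents give no figure to reproduce on this point. The check compares the sections, then asks what the planned tables can and cannot reveal.

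**Step 1. Sections side by side.**

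| Data | Change from baseline | Shift or new-abnormality summary | Subject listing |
|---|---|---|---|
| Laboratory (SAP 7.8.3) | Yes | Yes, selected tests | Yes |
| Vital signs (SAP 7.8.4) | Yes | No | Yes |
| ECG (SAP 7.8.5) | No | No | Yes |
| Physical examination (SAP 7.8.6) | Not applicable (normal/abnormal) | No | Yes, with details |

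**Step 2. What visit counts reveal.** Take n subjects seen at both visits, a abnormal at baseline and b abnormal at Day 91. Let x be the number normal at baseline and abnormal at Day 91. Then x cannot exceed b or n − a, and it cannot be below b − a or below 0. So x lies between max(0, b − a) and min(b, n − a).

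The arm sizes come from Protocol 5.3 (12:4 per cohort). The values of a and b are assumptions, since the documents give no expected abnormality rate.

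| n | a | b | Newly abnormal, lowest | Newly abnormal, highest |
|---|---|---|---|---|
| 12 | 3 | 3 | 0 | min(3, 9) = 3 |
| 12 | 6 | 6 | 0 | min(6, 6) = 6 |
| 12 | 9 | 9 | 0 | min(9, 3) = 3 |
| 12 | 6 | 9 | 9 − 6 = 3 | min(9, 6) = 6 |
| 4 | 2 | 2 | 0 | min(2, 2) = 2 |

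In the second row, identical planned tables would arise whether none or all of the 6 subjects normal at baseline became abnormal. A shift table gives x directly.

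**Step 3. Continuous ECG measures.** With complete data, the Day 91 mean minus the baseline mean equals the mean change, so the planned table already yields that number. It does not yield the SD, minimum or maximum of the individual changes, and with missing ECGs the two means come from different subjects.

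**Step 4. Precision, QTcF as an example.** Assume a total SD of 20 ms, n = 12, and within-subject deviations independent between visits. The SE of an observed mean is 20/√12 = 5.8 ms. The SE of a mean change is √2 × w/√12, where w is the within-subject SD. The variance ratio is 2w²/20².

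| w (ms) | SE of change (ms) | Variance ratio, change to observed |
|---|---|---|
| 8 | 3.3 | 0.32 |
| 10 | 4.1 | 0.50 |
| 14 | 5.7 | 0.98 |
| 16 | 6.5 | 1.28 |

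Break-even is w = 20/√2 = 14.1 ms. Neither SD is in the documents, and subjects whose rhythm differs between visits could have a larger w.

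**The case against.** The strongest reply is that old and new findings can be told apart from what is already planned. ECG results are listed by subject and visit, Day 1 included. Examination abnormalities are listed with their details, and SAP 7.5 adds a listing of abnormal screening examinations. Protocol 7.12 sends clinically significant ECG abnormalities to the adverse event form, and SAP 7.8.2 counts an event that began before dosing only if its severity worsens afterwards. With about 16 subjects per cohort, reading the listings is feasible. This stands. A reader might infer from the missing summaries that pre-existing atrial fibrillation cannot be distinguished from change on treatment at all; the documents do not support that. The listings nevertheless leave each reader to build the table, and the adverse event route does not summarise interval changes or a move from normal to abnormal without clinical significance.

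Four further replies also stand:

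- **The SAP does not depart from the protocol.** Protocol 8.6 asks only for ECG statistics by timepoint.
- **Endpoint status is weaker than SAP 3.2 suggests.** That section names ECG and physical examination as safety endpoints, but SAP section 1 cites protocol Version 2.0. Section 2.2 of the amended protocol names occurrence of adverse events and serious adverse events.
- **The share of subjects in atrial fibrillation at baseline is unknown.** Criterion 3 admits subjects by history. One cannot say that the abnormality counts mostly describe the disease, and the argument from the entry arrhythmia bears on the cardiovascular examination, not on all ten systems.
- **Summarising PR is not shown to be an error.** The number of subjects is reported with each summary, so unrecorded values drop out. Whether rhythm is a coded field depends on a case report form that is not among the documents.

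**Conclusion.** The concern holds as a gap in the summary tables. SAP 7.8.5 and 7.8.6 plan no change-from-baseline or shift summary, unlike the laboratory and vital-sign sections, although 7.8.5 and Protocol 8.6 both refer to an ECG baseline. The tables therefore cannot separate pre-existing from new abnormalities; only subject listings and treatment-emergent adverse events can.

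The size is modest. These are descriptive safety data, no test depends on them, and nothing is lost from the database. The illustrative range of 0 to 6 newly abnormal subjects out of 12 rests on assumed counts, but the fact that visit totals do not determine the number newly abnormal does not. A reader might also infer a fixed precision gain for QTcF, such as half the variance. That figure needs SDs which the documents do not give, and with a total SD of 20 ms the gain disappears once the within-subject SD passes about 14 ms.

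**What to change.** - **SAP 7.8.5:** add change from baseline for the six listed ECG measures at Day 91 and end of study, using the definition in SAP 6.1 with its fallback to screening when Day 1 is missing. Add a shift table of the three-category investigator interpretation from baseline to each of these visits.
- **SAP 7.8.6:** add, per body system, the number of subjects normal at baseline and abnormal after baseline, and keep the present visit counts. Worsening in a system already abnormal cannot be derived from a normal/abnormal field, so it stays with the listing of details and medical review.
- **SAP 7.8.3, 7.8.4 and 7.8.5:** change the baseline pointer from section 3.1 to 6.1.
- **Optional:** if rhythm is recorded, tabulate it at each ECG and restrict the PR summary to sinus rhythm.

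The cost is a few extra descriptive tables and their programming. No new assessment is needed. Only the optional item might require extraction from the ECG readings.
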